Experience of Principal Investigator: Brief summary (also attach a CV, biosketch, or Form 1572, if available)	
[name] is an internationally known researcher in embolization, particularly of uterine fibroids. His group has performed over 3000 uterine embolization procedures. He has a long history in managing both single center and multi-center clinical studies in embolization. He has performed similar Phase I and II studies in uterine embolization and his initial 1997 Georgetown IRB protocol for uterine embolization was the first such protocol in the country. He has long experience in safety studies, having studied the complication rates of the first 400 uterine embolization patients treated here and also as a co-investigator on the FIBROID Registry, a 3000 patient safety and efficacy registry.
 
[name] has visited centers in both Lisbon, Portugal and Sao Paulo, Brazil and has observed approximately 20 prostate embolization procedures during those visits. He also performed a prostate embolization under the tutelage of [name] at the University of Sao Paulo

Source of Funding/Grant Support for Project (if any) Please attach two copies of the Grant Application	Commercial Support (if any) for Project
None	

Has this study undergone previous scientific review?

Please note that **independent scientific review and approval** are **required** for all **DOD** sponsored studies.

Yes No

If yes, state where reviewed and attach documentation of approval

--

Investigational New Drug (IND)
 
 None
 
 IND: FDA # _____
 
 Drug Name: _____
 
 Drug Sponsor: _____
 
 Significant (SR)
 
 Non-Significant Risk (NSR)
	
Investigational Device Exemptions (IDE)
 
 None
 
X IDE: FDA No. G120220/A00
 
X Device Name: Embospheres Microspheres
 
 Device Sponsor: _____
 
Investigator sponsored _____
 
X Significant (SR)
 
 Non-Significant Risk (NSR)

--	--

If this project involves an FDA regulated drug or device, you must file an FDA form 3455. Please submit any communications from the FDA regarding IND, IDE, or humanitarian use applications related to this submission.

Phase I/II
Phase: I **II** **III** **IV** **Pilot**

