During the procedure conscious sedation with intravenous fentanyl and Versed will be provided. Ciprofloxacin 400 mg administered intravenously prior to the procedure for antibiotic prophylaxis. The procedure will be performed in the Interventional Radiology suite by one or both of the study investigators. A Foley catheter will be placed, with the balloon filled with contrast material to assist in prostate and bladder localization. Bilateral femoral arterial access will be obtained, unless evidence of vascular disease in the iliofemoral system precludes safe bilateral access. In that event, unilateral femoral access will be obtained. Each patient will have a selective internal iliac arteriogram, and as necessary, an arteriogram of the anterior division of the internal iliac artery performed to identify the prostatic arterial supply. This typically arises from the inferior vesicle artery (also known as the prostatic artery), but may have supply from the superior vesicle, the internal pudental or obturator branches as well.

The prostatic arteries will be selected using standard micro-catheter technique. Embolization of the prostate will be performed with 300 to 500 um sized TAGM (Embosphere® Microspheres, Merit Medical, South Jordan, UT). The embolization endpoint will be absence of the normal blush of the prostate on post embolization angiography and stasis of flow in the prostate arteries.

After the catheters are removed, hemostasis will be achieved with manual compression.

Post-Procedure Care

As the primary outcome is safety, each patient will be admitted for observation and short-term recovery overnight. Analgesics will be provided via IV PCA. During the observation period, each will be assessed on the severity of pain occurring during the first 24 hours after treatment using a visual analogue scale (VAS) administered by the nurse practitioner. The assessment sheet will include a 10 cm linear VAS scale along with subjective questions regarding the patients' degree of other symptoms, specifically rectal pain or bleeding, pain with urination or gross hematuria. After discharge, the patients will be called the next day to review symptom status and to screen for complications.

Follow-up Care and Evaluation

In the Table 2 below, the baseline and follow-up visits and the associated assessments at each visit are summarized.

Table 2. Study assessment summary

Prior to treatment	Procedure	1 week after treatment	3 months	6 months	12 months and annually

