Trans rectal ultrasound is the current standard imaging for the clinical assessment of the prostate gland [29]. Having said that, MRI can provide a more comprehensive assessment of the prostate size and tissue viability. Contrast-enhanced MRI provides a perfusion “map” of the prostate and allows the determination of the extent of infarction (or non-perfusion) of the prostate. The preliminary work in both Lisbon and Sao Paulo suggests that the greater the degree of de-vascularization of the prostate, the greater the volume reduction. This is likely to correlate with symptom improvement, although this requires confirmation. We believe that this study will provide preliminary data that can be used to help design studies to test that hypothesis.

Adverse Events

Each adverse event will be recorded as they occur. Each will be categorized as to type and severity using the Society of Interventional Radiology (SIR) definitions of adverse events based on outcome. That classification is as follows:

Type	Class	Definition
Minor	A	No therapy, no consequence
	B	Nominal therapy, no consequence; includes overnight admission for observation only.
Major	C	Require therapy, minor hospitalization (<48 hours).
	D	Require major therapy, unplanned increase in level of care, prolonged hospitalization (>48 hours).
	E	Permanent adverse sequelae.
	F	Death.

Analysis

The primary outcome is the absence of complications to the bladder, rectum or other pelvic structures detected in the first week after therapy. Each patient will be judged free of these adverse events or not. For those with an adverse event, the complication will be scored using the SIR definitions. Descriptive statistics will be used to summarize these events, along with patient demographics and initial clinical status.

Appropriate parametric and non-parametric tests will be used to assess change in laboratory measures, urine flowmetry parameters, and scores from the IPSS and IIEF. Changes in prostate volumes and the estimated volume of devascularized tissue will be calculated for each patient and outcomes from the different embolics will be compared. Appropriate paired parametric and non-parametric tests will be used to determine statistical significance. A p value of 0.05 will be considered statistically significant.

Statistical Considerations (justification for sample size or “n”, power or degree of change):

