Each significant injury to a patient's bladder or rectum will be reported immediately to the IRB staff. Those with lesser injuries will be recorded and followed to resolution. All minor and major complications will be summarized after each set of 10 patients and reported to the IRB. We currently plan to stop the study for re-evaluation of its overall safety if more than 20% of patients assessed after the first 10 patients (and each subsequent group of 10 patients) suffers either a bladder or rectal injury requiring surgical intervention.

We do not believe a data safety and monitoring committee is needed as our urology co-investigators will serve the role of safety monitors. They have a strong incentive to identify injuries, as they do not perform this procedure and it has the potential to compete with traditional therapies. While our urology colleagues are interested in providing alternatives to TURP for their patients, they have no interest in a therapy that is not safe.

7. Does a Data Safety and Monitoring Board exist?

Yes No

[A Data Safety and Monitoring Board, an independent group of experts, will review the data from this research throughout the study. Patients will be told about new information from this or other studies that may affect their health, welfare, or willingness to stay in this study.]

8. Does this study include a Placebo?

Yes No

9. Website Summary: If this is an open clinical trial, recruitment material for clinical trials and information for sponsors about the type of research we do will be posted on the Clinical Trials website. Please create a brief summary, in Layman Terms (8th grade language) of 200 words or less for this protocol outlining the salient features that may be useful to public and health care professionals.

<http://clinicaltrials.georgetown.edu/index.html>

The Departments of Radiology and Urology at Georgetown University Hospital are collaborating on a research study to determine the safety and effectiveness of prostate embolization, a new treatment for men who have enlarged prostate glands and urinary obstruction. Men with urinary obstruction usually have frequent urge to urinate, a weak urine stream, difficulty starting to urinate and may need to urinate numerous times each night.

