	Electrocardiograms (EKGs)		Exercise testing
	Intravenous glucose tolerance tests		Intravenous catheter insertion
	Magnetic resonance imaging (MRI) scans		Observational studies
	Oral glucose tolerance tests		Pathology slide review
	Special/prescribed diets		Venipuncture
	Other non-therapeutic tests or studies. Please list:		

Note: In the assignment of risk levels, a research survey may be considered more than minimal risk to subjects if dealing with very sensitive information.

10.2 Plans for Reporting of Adverse Events Including Subject’s Death.

Adverse events from this protocol will need to be reported to the IRB, GCRC RSA (if the study is being conducted on the GCRC), and GCRC Nurse Manager (if the study is being conducted on the GCRC). In the section below, please list other individuals and/or entities to whom adverse events will be reported.

Individual/Entity	
	Investigator
	National Institutes of Health and/or
	Food and Drug Administration (FDA)
	Other agency or sponsor
	Please specify:

10.2.1 Who is the individual/entity primarily responsible for AE and to whom they are primarily reported.

Name	Position
[name]	Principal Investigator

Plans for Monitoring the Progress of Trials and the Safety of Participants

10.2.1 Safety tests. In the section below, please indicate the summary of safety tests, particularly those that screen out ineligible research subjects and those that monitor for toxicity and other adverse outcomes.

Clinical evaluation will be used before to exclude those that have renal insufficiency, iliac artery occlusion, and prostate cancer.
 
Office anoscopy and cystoscopy will be completed before the procedure and at regular intervals after to evaluate the bladder and rectal mucosa. This is the most sensitive test to detect ischemic injury.

All X-ray parameters will be recorded to estimate patient exposure. At the 1 week and 3 month office visits, each will have the skin of the buttock assessed, as this is the most likely site for an radiation injury and it should be manifest between 1 week and 3 months after exposure.

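### Non-operating urologists replace a monitoring board, but adverse events go primarily to the embolization-side principal investigator and no one is named to judge the primary outcome, grade events or apply the stopping rule

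*Combined protocol and SAP*

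**What the plan says.** Under Risk Minimization (item 6), the reason for having no board is: "We do not believe a data safety and monitoring committee is needed as our urology co-investigators will serve the role of safety monitors". Of these urologists it adds: "They have a strong incentive to identify injuries, as they do not perform this procedure". Section 10.4.6 repeats that urology staff are the safety monitors.

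The adverse-event reporting part of section 10 asks "Who is the individual/entity primarily responsible for AE and to whom they are primarily reported". The single entry is the principal investigator. Section One places that person in Radiology and describes an "internationally known researcher in embolization, particularly of uterine fibroids". On who operates, the Procedure section says: "The procedure will be performed in the Interventional Radiology suite by one or both of the study investigators".

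The primary outcome is freedom from bladder, rectal or other pelvic complications found within the first week. The Primary objective and Analysis paragraphs both say: "Each patient will be judged free of these adverse events or not". On grading, the Adverse Events section says: "Each will be categorized as to type and severity using the Society of Interventional Radiology (SIR) definitions of adverse events based on outcome". These statements name no judge and no grader. Section 10.4.5 gives a stopping criterion but does not say who checks it.

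There is parallel reporting. Section 10.2 says: "Adverse events from this protocol will need to be reported to the IRB". Bladder or rectal injuries needing surgery are reported to the IRB at once, and all complications, minor and major, are summarized to it after every ten patients.

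**The concern.** The case for having no board rests on one feature: the monitors are not the operators. That feature protects the primary result only if the monitors take part in producing it, by deciding whether a finding counts, grading it and checking the stopping criterion. The text available attaches the monitors to none of these steps, and the one named recipient of adverse events is on the embolization side.

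The yes/no call leaves room for judgement. The study inspects bladder and rectal mucosa at one week to find injuries that clinical experience may have missed, so borderline findings are to be expected. With one arm, no blinding and 30 men, a few such calls could set the headline safety rate.

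**Working it through.** **1. Who is assigned what**

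| Task | Where | Assigned to |
|---|---|---|
| Safety monitoring in place of a board | Item 6; 10.4.6 | Urology co-investigators or staff |
| Primary responsibility for and receipt of adverse events | 10.2.1 | Principal investigator (Radiology) |
| Embolization | Procedure | Study investigators, in the Interventional Radiology suite; not the urologists (item 6) |
| Yes/no primary judgement | Primary objective; Analysis | Not named |
| SIR class | Adverse Events | Not named |
| Checking the stopping criterion | 10.4.5 | Not named |
| Baseline cystoscopy and anoscopy | Pre-procedure Patient Evaluation | Urology clinic |
| Receipt of complication reports | Item 6; 10.2; 10.4.6 | IRB |

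The first two rows can coexist: the investigator can hold regulatory responsibility while others monitor. The gap is in the three unassigned rows, and in the lack of any stated route by which adverse events reach the monitors. Part of section 10, between 10.2.1 and 10.4.4, was not in the text available for this review and should be checked for an assignment.

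**2. How far one call moves the result**

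The plan ties no power, precision or error rate to its 30 patients, so it has no figure to reproduce. With n = 30, one changed call moves the rate by 1/30 = 3.3 percentage points. Exact (Clopper-Pearson) 95% limits for x events are:

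- lower = Beta quantile(0.025; x, n − x + 1), and 0 when x = 0
- upper = Beta quantile(0.975; x + 1, n − x)

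Results:

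- x = 2: 2/30 = 6.7%, 95% CI 0.8 to 22.1%
- x = 0: 0/30 = 0%, upper limit 1 − 0.025^(1/30) = 11.6%, so 0 to 11.6%

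Two men called free of complication rather than affected would lower the estimate by 6.7 points and the upper limit by 22.1 − 11.6 = 10.5 points.

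**3. What does not move it**

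The primary outcome counts patients with or without a complication. Moving an event from one SIR class to another changes the severity table but not x/30.

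**4. Whether borderline findings are plausible**

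The rationale cites a 12-patient series reported as free of major complications, in which 3 had minimal rectal bleeding and 1 had focal bladder ischemia. If those rates carried over (an assumption; all of those men had catheter-dependent retention), 30 men would give 30 × 3/12 = 7.5 with bleeding and 30 × 1/12 = 2.5 with ischemia. Whether such findings count could decide the headline rate.

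**The case against.** A reader might infer that the plan lets the operators decide which events count and how they are graded. The documents do not support that. The judging and grading sentences are in the passive voice, and receiving reports is not adjudicating them. The entry naming the principal investigator answers a form question about responsibility and need not conflict with urologists acting as monitors.

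There are also real counterweights:

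- Section 10.4.6 confirms the urologists' role.
- The IRB receives every complication in ten-patient summaries, and the injuries needing surgery at once.
- Baseline endoscopy is done in the urology clinic, and Table 2 lists a urologic exam and cystoscopy at one week and again at 3, 6 and 12 months.
- SIR classes depend on outcome, and Class A gives an event without therapy or consequence a place, so it need not be dropped.
- The stopping criterion turns on surgery, a comparatively hard event.

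All of this stands and limits the point. It does not close the gap. No section asks the IRB to adjudicate; it is sent summaries of events already identified as complications. Finding a mucosal change is not the same as deciding whether it is a complication. An outcome-based scale grades events once they have been counted, but does not say who counts them.

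**Conclusion.** The point holds in limited form. The plan justifies having no board by the monitors' separation from the operators, but in the text available it does not carry that separation into the primary yes/no judgement, the SIR class or the stopping check. Nothing there prevents the operating team from doing all three.

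This allows bias and does not demonstrate it. A reader might take 2/30 against 0/30 as an estimate of bias. It is not: it assumes two changed calls, and such sensitivity would apply to any 30-patient series. It shows only that each yes/no call is worth 3.3 points.

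The conclusion assumes that the missing part of section 10 does not assign these tasks, and that the principal investigator belongs to the operating side. The Radiology post and embolization background support the second assumption, but the Procedure section does not say which investigators operate. The change is a cheap improvement; the design does not fail without it.

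**What to change.** In the Adverse Events and Analysis sections and in 10.2.1 and 10.4.6, state that:

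- adverse events go to the urology monitors as well as to the principal investigator and the IRB;
- a urology co-investigator who took no part in that patient's embolization makes and signs the yes/no primary judgement and the SIR class, from the endoscopy and clinical records, and signs the ten-patient report;
- the principal investigator keeps regulatory responsibility, and any differing opinion is recorded and reported beside the urologist's.

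In 10.4.5, state that the urology monitors check the stopping criterion. First reconcile it with item 6: item 6 sets the threshold above 20% of a group of ten (at least three patients), while 10.4.5 sets it at two in any ten.

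The cost is protocol wording and a little urologist time, with no new staff, visits or tests. The downside is small: the urologists are co-investigators, and item 6 notes that the procedure may compete with traditional therapies. They are separate from the operators but not independent of the study, and any error would tend toward counting an injury.

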10.4.4 Safety Monitoring Methods and Intervals

In the section below, please check all that apply.

Data to be Evaluated	Interval/Frequency of Evaluation*
 Age specific intervention(s)	1 week after treatment, 3 months, 6 months, 12 months and annually for 5 years.
 Clinical test(s)	
 Subject interview and/or contact	
X Subject's physical exam	
 Subject's symptoms or performance status	
 Subject's vital signs	
X Other study parameters. Please list: 	

10.4.5 Decision Making Criteria and Stopping Rules

In the section below, please describe data safety monitoring criteria for decision-making regarding continuation, modification, or termination of the clinical study.

The study will be stopped if any two patients in any 10 patients suffer either a bladder or rectal injury requiring surgical intervention. Thus if in the first 10 patients, two patients have this type of injury, the study will be stopped. Similarly, if two patients in any set of 10 patients has this type of injury, the study will be stopped. After each 10 patients, a report on complications will be submitted to the IRB.

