Pisco's group also just presented the results of 152 patients at the same SIR meeting in March 2012 [28], although these results are not yet published. The procedure was technically successful in 144 of 152 patients. Follow-up of between 3 and 30 months was available in 102 patients. Clinical success was noted in 84.3% at 3 months and in 38 of 46 (82.6%) at 12 months. These authors reported no major complications beyond the bladder wall ischemia noted in their initial published report. They did report a number of minor complications, although they did not report the frequency in the published abstract. These included burning in the urethra, urinary infection, hematuria, hemospermia, balanoprostitis, rectorrhagia, inguinal hematoma and pain. These initial reports suggest that prostate embolization is feasible and the initial results suggest that improvement in symptoms occurs in the majority and that shrinkage in prostate volume is likely. The safety is somewhat less certain. While major complications are likely rare, it is unclear how frequently minor injuries to the bladder and rectal mucosa occur. We believe it is important to confirm the safety of this procedure in practice in a well-designed study in the US, with careful evaluation and follow-up of each patient prior to the development of a larger trial or acceptance of this procedure into practice. The materials used in these procedures have FDA clearance for other indications and are readily available for interventionalists to use in this treatment. To date there has been no clinical trial completed in the United States and we believe that an assessment of this treatment in clinical studies is essential before its adoption into practice.

References

1. Blake-James, B.T., et al., *The role of anticholinergics in men with lower urinary tract symptoms suggestive of benign prostatic hyperplasia: a systematic review and meta-analysis*. BJU Int, 2007. **99**(1): p. 85-96.
2. Lourenco, T., et al., *Alternative approaches to endoscopic ablation for benign enlargement of the prostate: systematic review of randomised controlled trials*. Bmj, 2008. **337**(jun30 1): p. a449.
3. Yang, Q., et al., *Transurethral incision compared with transurethral resection of the prostate for bladder outlet obstruction: a systematic review and meta-analysis of randomized controlled trials*. J Urol, 2001. **165**(5): p. 1526-32.

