We cannot accurately estimate the risk of bladder or rectal injury as detailed analysis of the currently reported patient experience has not been reported. We have visited both the group in Lisbon, who have now treated over 250 patients and the Brazilian group has treated over 70 patients. There have been no serious rectal injuries reported. There has been one injury in the Lisbon group to the bladder that resulted in the need for bladder resection.

Therefore, the current experience would suggest that the risk of complication is low, with the risk of a serious complication is extremely low (less than 1% chance) but that is based on clinical experience and not careful assessment of the rectum and bladder. This is the main focus of our study

Based on the reported data to date and known potential complications of angiographic procedures, the following are potential risks of the procedure:

Related to the embolization of the prostate: Minor or self-limited complications: burning in the urethra, urinary

infection, hematuria, hematospermia, hemorrhage, vasospasm, rectorrhagia, pain in the pelvis, or allergic reaction to embolic material.

More serious complications related to embolization of the prostate: bladder or bladder neck necrosis, possibly requiring surgical resection. Bladder ischemia causing severe pain, but resolving without complication. Other than the one case of surgical resection of the bladder in Lisbon, all reported complications have resolved with minimal or no therapy.

Complications related to angiography: arterial injury, which in rare instances (<1%) can lead to need for surgical repair of the artery, arterial injury in the pelvis, puncture site hematoma and allergic reaction to the contrast media.

Radiation injury to the skin of the buttocks- this complication is not yet reported but is possible with prolonged procedures.

Risk Minimization

As noted above, great care will be taken with the use of X-ray exposure to minimize dose. Similarly, each patient will be evaluated pre-procedure for sedation risk according to the standard of care and will be followed by both the interventional radiology and urology staff physicians.

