10.4.6 Monitoring of the Study

In the section below, indicate who will monitor the study and to whom the study will report. Describe the frequency of the monitoring. If a DSMB is required, describe the composition of the board, its role, and the frequency of meetings and methods of communications.

The urology staff will serve as safety monitors. Each significant injury (requiring surgical intervention) to a patient's bladder or rectum will be reported immediately to the IRB staff. Lesser injuries will be recorded and followed to resolution. All minor and major complications will be summarized after each set of 10 patients and reported to the IRB.

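### The safety stop is written two ways: item 6 needs at least 3 surgical injuries in 10 patients, section 10.4.5 needs 2

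*Combined protocol and SAP*

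**What the plan says.** Two places set a stopping threshold for bladder or rectal injury that needs surgery.

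- **Section Three, item 6 (Risks, Risk Minimization).** The investigators intend, for now, to "stop the study for re-evaluation of its overall safety if more than 20% of patients assessed after the first 10 patients" have such an injury. The same check is repeated for every later group of 10.
- **Section 10.4.5 (Decision Making Criteria and Stopping Rules).** "The study will be stopped if any two patients in any 10 patients suffer either a bladder or rectal injury requiring surgical intervention". The section then gives an example in which two such injuries among the first 10 patients stop the study, and adds: "Similarly, if two patients in any set of 10 patients has this type of injury, the study will be stopped".

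Section 10.4.6 provides that "Each significant injury (requiring surgical intervention) to a patient's bladder or rectum will be reported immediately to the IRB staff". Item 6 has the same immediate reporting for significant injuries, and complications are also summarized for the IRB after each 10 patients.

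On the expected rate, item 6 says that "the risk of a serious complication is extremely low (less than 1% chance"), and notes that this rests on clinical experience without careful assessment of the rectum and bladder. The rationale section says: "While major complications are likely rare, it is unclear how frequently minor injuries to the bladder and rectal mucosa occur".

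**The concern.** The event is the same in both places and so is the group size of 10. Only the threshold differs. Two of 10 is exactly 20%, so it meets the 10.4.5 trigger and does not exceed the 20% in item 6. A reader who has only item 6 in hand would not treat 2 of 10 as a reason to stop, although that is the very case 10.4.5 uses as its example.

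Safety is the primary goal of the study, and these are the only numerical stopping criteria in the text available for review. Item 6 also declines a data safety and monitoring committee and gives the monitoring role to the urology co-investigators. With no such committee to interpret an ambiguous rule, the written threshold should have one value.

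**Working it through.** **1. Thresholds as counts.** The smallest k with k/10 > 0.20 is 3. The smallest k with k/10 ≥ 0.20 is 2. The count in 10.4.5 therefore follows from item 6 only if item 6 had said 20% or more. The plan gives no operating characteristics for either rule, so there is no plan figure to reproduce.

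**2. Inputs.**
- 30 patients, that is three groups of 10 (Duration of investigation).
- True rate of surgical injury, p. The plan supports three values:
  - About 1 in 320: one case, "There has been one injury in the Lisbon group to the bladder that resulted in the need for bladder" resection, among over 250 Lisbon and over 70 Brazilian patients (item 6).
  - 1 in 152: the same single case over the 152-patient presentation in the rationale section, assuming that series includes it.
  - 1%: the top of the plan's range for serious complications.
- Rates of 2%, 3%, 5% and 10% are assumptions, added to show what happens if the expectation is wrong.

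**3. Formulas.** With X ~ Binomial(10, p):
- P(X ≥ 2) = 1 − (1−p)^10 − 10p(1−p)^9
- P(X ≥ 3) = P(X ≥ 2) − 45p²(1−p)^8
- Stop in any of three fixed groups = 1 − (1 − P)³

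10.4.5 can also be read as any 10 consecutive patients, so that two injuries fewer than 10 patients apart stop the study. Counting the arrangements of 0, 1, 2 or 3 injuries in 30 patients with every pair at least 10 apart gives 1, 30, C(21,2) = 210 and C(12,3) = 220. Four cannot fit. So

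P(stop) = 1 − [(1−p)^30 + 30p(1−p)^29 + 210p²(1−p)^28 + 220p³(1−p)^27].

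**4. Worked case, p = 5%.**
- P(X ≥ 2) = 1 − 0.5987 − 0.3151 = 0.0861
- P(X ≥ 3) = 0.0861 − 0.0746 = 0.0115
- Item 6, three groups: 1 − (1 − 0.0115)³ = 3.4%
- 10.4.5, three groups: 1 − (1 − 0.0861)³ = 23.7%
- 10.4.5, any 10 consecutive: 1 − (0.2146 + 0.3389 + 0.1249 + 0.0069) = 31.5%

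**5. Chance of a stop over 30 patients.**

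| True rate | Basis | Item 6, ≥3 per fixed group | 10.4.5, ≥2 per fixed group | 10.4.5, any 10 consecutive | Gap, fixed groups (points) |
|---|---|---|---|---|---|
| 1/320 | plan | 0.001% | 0.13% | 0.21% | 0.13 |
| 1/152 | plan | 0.01% | 0.56% | 0.91% | 0.55 |
| 1% | plan | 0.03% | 1.3% | 2.0% | 1.24 |
| 2% | assumed | 0.26% | 4.8% | 7.2% | 4.5 |
| 3% | assumed | 0.83% | 10.0% | 14.4% | 9.2 |
| 5% | assumed | 3.4% | 23.7% | 31.5% | 20.3 |
| 10% | assumed | 19.6% | 60.1% | 69.4% | 40.5 |

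**6. Other reading of item 6.** If its percentage is taken cumulatively, it needs 3 of 10, 5 of 20 or 7 of 30. The chance of a stop is then 1.3% at a 5% rate and 9.6% at a 10% rate, so the gap widens.

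**The case against.** The best reply is that the two texts do not collide in operation. Item 6 does not order the study to continue at 2, so stopping at 2 obeys both. Section 10.4.5 is the field meant for stopping rules, is worded as mandatory and gives an example at exactly 2 of 10. Item 6 is a statement of current plans inside a narrative on risk. The IRB hears of each surgical injury immediately, so a second one could not pass unnoticed. At the rates the plan expects, the two rules differ by at most 1.24 points with fixed groups, and the large gaps come from assumed rates at least five to ten times the plan's ceiling. On this view it is a small drafting slip.

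Most of that stands, and it limits the seriousness of the point. It does not remove the inconsistency. Immediate reporting makes the injuries visible but does not settle whether two of them oblige a stop. A stopping rule is there for the case in which the expected rate is wrong, and item 6 itself says the risk of bladder or rectal injury cannot be estimated accurately. Nor does a two-tier reading help: the pause for re-evaluation would then need more injuries than the outright stop, and no such scheme is described.

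Two further caveats are fair. That item 6 is the text in error is an inference from the status and the example of 10.4.5. And a short part of the protocol ahead of 10.4.4 was not available for review, so the absence of a reconciling statement applies to the rest.

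**Conclusion.** The inconsistency is real and lies in a decision threshold: at least 3 of 10 in item 6, at least 2 of 10 in section 10.4.5, for the same injury. It should be corrected. Harm would arise only if someone applied item 6 alone and did not treat 2 of 10 as a stop, and it would matter only if surgical injury were several times more frequent than expected. With fixed groups the difference in the chance of a stop is about 1.2 points or less at the plan's own rates, about 20 points at 5% and about 41 points at 10%. These figures assume independent patients with a common injury rate and all 30 patients treated. The finding that the thresholds differ needs none of those assumptions.

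**What to change.** Edit item 6 only. Replace its 20% condition, including the parenthesis on later groups, with *two or more of any 10 patients (20% or more) suffer*, and end the sentence with *as set out in section 10.4.5, which governs*. Leave the threshold, window and consequence in 10.4.5 unchanged. The cross-reference also settles whether the consequence is a pause for re-evaluation or a stop. It does not settle whether the 10 patients are fixed groups or any 10 consecutive patients. That question is already present in 10.4.5.

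The cost is one sentence, with no added patients, visits or procedures. Compared with item 6 as written, the chance of stopping at a true rate of 1% rises from 0.03% to 1.3% with fixed groups, or to 2.0% with any 10 consecutive patients. Section 10.4.5 already accepts that.
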